5.3. Maintaining the Study Blind

In this double-blind study, all personnel involved, i.e. physicians, site staff, and participants will remain blinded at all times, except in an emergency where knowledge of the randomization code is required to provide appropriate treatment. The SMC will remain blinded but may break the blind for a given subject if deemed justified in accordance with the committee charter.

Preparation of the randomization schedule in accordance with Avance SOP S-DM-004 (Randomization) was performed by staff members of Avance who have no responsibility for monitoring and data management of this study.

The individual data listings for inclusion in an appendix to the report will be prepared after the study has been unblinded.

5.4. Assessment Time Point Identifiers

In the data listings for the report, scheduled assessment time points will be identified as follows:

- Scheduled safety assessments will be identified by treatment, study day, and also nominal study time point, where relevant.
- Pharmacokinetic assessments will be identified by nominal time post-dose for the study treatment period.
- Assessments at Screening and Study Completion visit will be identified as such for both study day and time-point, as appropriate.

5.5. Data Derived by Calculation

The following data fields for inclusion in the data listings will be derived by calculation:

AEs Single Period:

- Treatment-emergent Indicator for adverse event, assigned as Treatment-Emergent if

$(\text{Onset Date} + \text{Onset Time}) \geq (\text{Date of First Dose} + \text{Time of First Dose})$

Non Treatment-Emergent if

$(\text{Onset Date} + \text{Onset Time}) < (\text{Date of First Dose} + \text{Time of First Dose})$

- Adverse event time since first dose (in days, to two decimal places), calculated as $(\text{Onset Date} + \text{Onset Time}) - (\text{Date of First Dose} + \text{Time of First Dose})$
- Adverse event time since dose in current treatment period (in days, to two decimal places), calculated as $(\text{Onset Date} + \text{Onset Time} - \text{Date of Dose in Current Treatment Period} - \text{Time of Dose in Current Treatment Period})$

AE Duration:

- Adverse event duration (in days, to two decimal places), calculated as $(\text{Resolution Date} + \text{Resolution Time} - \text{Onset Date} - \text{Onset Time})$

Safety Assessments Change from Baseline:

- Baseline for Vital Signs, ECG parameters, serum clinical laboratory parameters will be the most recent scheduled assessment prior to first dose

Clinical Laboratory Assessments:

- If a clinical laboratory result is above the upper limit of normal, then Out of Range flag will be set to “H”
- If a clinical laboratory result is below the lower limit of normal, then Out of Range flag will be set to “L”
- Clinical Laboratory parameters that are outside the reference range and assessed as clinically significant will be identified as “Abnormal CS”
- Clinical Laboratory parameters that are outside the reference range and not assessed as clinically significant will be identified as “Abnormal NCS”

Pharmacokinetics:

- Actual collection time post-dose (in hours, to two decimal places) for PK blood samples for each dose day calculated as $(\text{Collection Date} + \text{Collection Time} - \text{Date of Dose} - \text{Time of Dose})$

Pharmacodynamics:

- Actual collection time post-dose (in hours, to two decimal places) for PD CSF samples for each dose day calculated as $(\text{Collection Date} + \text{Collection Time} - \text{Date of Dose} - \text{Time of Dose})$

Efficacy Assessments Change from Baseline:

- Baseline for ADAS-Cog11, ADAS-Cog13, ADAS-Cog14, NTB, ADCS-ADL, MMSE, CDR-SB, and ADCS-CGIC will be the most recent scheduled assessment prior to first dose

Efficacy Assessments:

- MMSE Total Score = sum of the individual scores from the 11 questions on the scale.
- The ADAS-Cog11 total score = the sum of all 11 individual items (word recall; commands; constructional praxis; naming objects and fingers; ideational praxis; orientation; word recognition; remembering test instructions; spoken language; word finding; and comprehension of spoken language). The ADAS-Cog 11 will be considered the primary cognitive endpoint for this study.
- The ADAS-Cog13 total score includes all of the items in the ADAS-Cog11 and the delayed word recall and the number cancellation.
- The ADAS-Cog14 total score includes all of the items in the ADAS-Cog13 and the maze item.
- The Cognitive Composite score will be calculated using z-scores of the below items. The z-scores will be derived by calculating the baseline mean and standard deviation of each individual component for all subjects. A z-score within each component will be derived for each subject at each timepoint by subtracting the corresponding baseline mean and then dividing by the corresponding baseline SD. The Cognitive Composite score will be set as the mean of the 10 individual z-scores within each subject and timepoint. If a subject is missing one, two, or three scores at a particular timepoint, the missing scores will be set as the average non-missing z-score of all subjects at that timepoint within each component when deriving the Cognitive Composite score. If a subject is missing four or more individual components at each timepoint, the Cognitive Composite score will not be derived.

ADAS-COG

Word recall (scored on a 0 to 30 range), sum of trials I, II, and III. If at least one of the trials is missing, this component will be considered missing. The sign of the z-score for this component will be reversed when deriving the Cognitive Composite score as it is the total words not recalled that is being recorded. This test is a key measure of episodic memory.

Orientation (0 to 8). The sign of the z-score for this component will be reversed when deriving the Cognitive Composite score as the recorded score for this test is the number of items answered incorrectly. This measure is an index of the study participant's episodic memory and a single item of semantic memory (their name).

Delayed Word Recall (0 to 10). The sign of the z-score for this component will be reversed when deriving the Cognitive Composite score as it is the total words not recalled that is being recorded.

Word Recognition (0 to 24). The sign of the z-score for this component will be reversed when deriving the Cognitive Composite score. This is a further test of episodic memory using a word recognition paradigm of 12 true positive targets and 12 foil items. While the possible score for this measure is 0 to 24, the standard ADAS-Cog score is capped at a maximum worst score of 12.

Number Cancellation (0 to c.40). This test was added to the original ADAS-Cog to remedy the absence of an attentional test. Performance can range between a score of 0 and c.40. ADAS-Cog scoring requires that ‘False alarms’ be subtracted from ‘hits’ to yield a score which is reported as 0 to 5 for ADAS-Cog scoring purposes. Having ensured that the total number of false alarms are comparable across both arms of the study, we will analyze total hits. If false alarms are unbalanced across study arms then the statistic ‘D’ will be calculated using Signal Detection Theory.

Maze - The ADAS-Cog14 augments the ADAS-Cog11 with delayed free recall, number cancellation, and maze-completion measures. A score of 0 to 10 for delayed free recall and a conversion code of 0 to 5 for the digit cancellation and maze completion provides total score ranges for the extended ADAS-Cog14 from 0 to 90. The Maze item will be included as one of the components when deriving the Cognitive Composite and Attention Composite score. The sign of the z-score for this component will be reversed when deriving these composite scores.

NTB

CFT – This is a further test of working memory and executive function that yields a key metric referred to as ‘Total number of acceptable words’. This is obtained by calculating how many of the study participant’s responses are deemed acceptable according to the scoring rules. The usual performance range for this test is between 0 and 40.

Digit Span – This is a brief measure of working memory, especially in the Digits Backwards section. The key metric is ‘Total number of trials correct’, which is the number of sequences correctly recalled. The range of the test is 0 to 24 and both floor and ceiling effects are rare.

Trail Making Test (TMT) A – This is essentially a measure of attention, as successful completion relies on quickly and accurately connecting numbered circles in an ascending sequence. The key metric for analysis purposes is ‘Time taken for completion’. Errors and time taken once again both contribute to performance. However, because errors incur a time penalty, it is not necessary to analyze both metrics. The sign of the z-score for this component will be reversed when deriving the Cognitive Composite score.

TMTB – This is the more complex component of the TMT in which successful completion relies on the study participant accurately connecting the numbered and lettered circles. Study participants are required to alternate between numbers and letters in an ascending sequence. The key metric for analysis purposes is again ‘Time taken for completion’. As with TMT A, because errors incur a time penalty, it is not necessary to factor in errors for analysis purposes. The sign of the z-score for this component will be reversed when deriving the Cognitive Composite score.

- The Memory composite score will be a composite z-score average similar to the Cognitive Composite score, but will only be derived using the average of the

ADAS-Cog Word Recall, Orientation, Delayed Word Recall, and Word Recognition items. If a subject is missing any of the four items at a timepoint, this composite score will not be derived.

- The Attention composite score will be a composite z-score average derived using the average of the Number Cancellation, Maze item from ADAS-Cog 14, and TMT A items. If a subject is missing either of the three items at a timepoint, this composite score will not be derived.
- The Executive function composite score will be a composite z-score average derived using the average of the CFT, Digit Span, and TMT B items. If a subject is missing any of the three items at a timepoint, this composite score will not be derived.

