### ***17.9 Missing, Unused and Spurious Data***

No imputation will be applied for missing data. Only non-missing values will be used for analyses.

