5.2. Randomization and Subject Identification Code

This is a double-blind, placebo-controlled study. Study drug will consist of either of two doses of CT1812 or placebo. The placebo will be identical in appearance to both doses of the active CT1812.

The non-blinded statistician assigned to the trial will generate a list with the appropriate number of 4 digit individual study IDs randomly for each arm, randomly assigned to either CT1812 300 mg, CT1812 100 mg or placebo treatment in a 1:1:1 ratio. Randomization will include a stratification factor for the MMSE score (18-22 or 23-26).

The Randomisation Number will be specified as Rrnnn, where:

- nnn = sequential subject id from 001 to 999,

In the listings presenting the individual data, subjects will be identified by randomization number, with dose of CT1812 as a secondary grouping identifier. The screening number will be shown only on the listing of informed consent data.

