 - If the Day 1 pre-dose concentration is missing and the analyte is not endogenous, then a value of zero will be imputed;

Efficacy missing data rules:

- The ADAS-Cog11 total score ranges from 0-70 with higher scores indicating greater dysfunction. When the total score is missing due to non-cognitive reasons for one of the questions, the total score will be calculated as a weighted average of the scores provided for the remaining ten questions as follows:
 - $\text{Imputed Total} = \text{Observed Total Score} * (1 + \text{Maximum Score of the missing value} / \text{Sum of the Maximum Score of the non - missing values})$

Calculation of Imputed ADAS-Cog-11 Total Score

Missing Question	Imputed Total formula
Word Recall	$\text{Observed Total} * (1 + 10/60)$
Orientation	$\text{Observed total} * (1 + 8/62)$
Word Recognition	$\text{Observed total} * (1 + 12/58)$
All other questions	$\text{Observed total} * (1 + 5/65)$

In cases where 2 or more questions are missing, the total score will not be imputed and will be set to missing.

- The ADAS-Cog-13 total score ranges from 0-85. The imputed total score when there is only one item is missing due to non-cognitive reasons is presented below:

Calculation of Imputed ADAS-Cog-13 Total Score

Missing Question	Imputed Total formula
Word Recall	Observed Total*(1+10/75)
Orientation	Observed total*(1+8/77)
Word Recognition	Observed total*(1+12/73)
Delayed Word Recall	Observed total*(1+10/75)
All other questions	Observed total*(1+5/80)

- The ADAS-Cog-14 total score ranges from 0-90. The imputed total score when there is only one item is missing due to non-cognitive reasons is presented below:

Calculation of Imputed ADAS-Cog-14 Total Score

Missing Question	Imputed Total formula
Word Recall	Observed Total*(1+10/80)
Orientation	Observed total*(1+8/82)
Word Recognition	Observed total*(1+12/78)
Delayed Word Recall	Observed total*(1+10/80)
Maze	Observed total*(1+12/78)
All other questions	Observed total*(1+5/85)

- No further imputation for efficacy assessments. In order to have all subjects with any non-missing efficacy data contributing to the analysis, a mixed model for repeated measures (MMRM) will be used to take the missing data into account. Under the assumption that missing data are missing at random, inferences based on methods of MMRM estimation in mixed models are valid.

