11.8. Changes from the Analysis Planned in the Protocol

There are no changes from the planned analysis described in the protocol.

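### The SAP imputes cognitive scores where the protocol allows no imputation yet declares no changes, and it leaves the Number Cancellation metric to an undefined comparison between arms

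*SAP*

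**What the plan says.** **Missing cognitive data.** Protocol 17.9 reads, in full: "No imputation will be applied for missing data. Only non-missing values will be used for analyses". SAP 5.5 builds the Cognitive Composite as the mean of ten component z-scores. With one to three missing at a visit, "the missing scores will be set as the average non-missing z-score of all subjects at that timepoint within each component"; with four or more missing, the score is not derived. The average is over all participants, so the arms are pooled. The Memory, Attention and Executive composites get no such fill: each is left missing if any of its items is missing.

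SAP 5.6 adds a second rule. For ADAS-Cog11, which SAP 5.5 names as the primary cognitive endpoint, if one item is missing for a non-cognitive reason "the total score will be calculated as a weighted average of the scores provided for the remaining ten questions". Similar tables follow for ADAS-Cog13 and ADAS-Cog14. The results are labelled imputed totals, and the closing bullet begins "No further imputation for efficacy assessments". SAP 11.8 then states: "There are no changes from the planned analysis described in the protocol".

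**Number Cancellation.** SAP 5.5 says: "Having ensured that the total number of false alarms are comparable across both arms of the study, we will analyze total hits". Otherwise a signal-detection statistic D replaces total hits. The Attention Composite is the "average of the Number Cancellation, Maze item from ADAS-Cog 14, and TMT A items". The trial has three arms: SAP 5.2 has participants "randomly assigned to either CT1812 300 mg, CT1812 100 mg or placebo treatment in a 1:1:1 ratio".

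**The concern.** Two governing documents give different instructions for the same missing scores, including those of the primary cognitive endpoint, and the SAP section meant to record such differences says there are none. A reader of the study report could not tell which rule was meant to apply. The composite fill also has a predictable effect: the inserted value is the same for every arm, so that part of the score carries no treatment contrast.

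The Number Cancellation rule is a different kind of problem. False alarms are themselves a post-randomisation outcome that treatment could affect. Choosing the metric by comparing them between arms leaves the definition of an endpoint open until data grouped by treatment have been seen.

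**Working it through.** The plan gives no figure to reproduce here. Its only power statement concerns PET synaptic density. It also gives no rate of missing components, so the rates below are assumptions.

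**1. The texts side by side.** Protocol 17.9 has no exception for item-level scoring and does not defer to the SAP, whereas Protocol 17.4 and 17.6 do defer covariates, correlation details and the Cochran-Mantel-Haenszel test. SAP 5.6 itself describes the ADAS-Cog rule as imputation.

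**2. Effect of the composite fill.** Let a fraction *f* of each arm miss *k* of ten components, with the missed tests chosen at random, and let the true contrast be δ. An affected participant's score keeps (10 − k)/10 of δ, so the expected contrast is (1 − f)δ + f(10 − k)δ/10 = δ(1 − fk/10).

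| f | k | Fraction kept |
|---|---|---|
| 0.2 | 1 | 1 − 0.02 = 0.98 |
| 0.2 | 2 | 1 − 0.04 = 0.96 |
| 0.2 | 3 | 1 − 0.06 = 0.94 |
| 0.5 | 3 | 1 − 0.15 = 0.85 |

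A simulation agrees: 0.978, 0.959, 0.939 and 0.840. It used 14 versus 7 participants, ANCOVA on change with baseline, component correlation 0.4, retest correlation 0.7 and an effect of 0.5 baseline SD on every component (all assumed except the group sizes). At f = 0.2 and k = 3 the loss is 0.06 × 0.52 ≈ 0.03, against a standard error of 0.24. Power with the fill was 0.529, 0.518, 0.532 and 0.504, against 0.532, 0.523, 0.549 and 0.540 with full data. Type I error was 0.047 to 0.059 with the fill, the same range as with full data.

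**3. Is averaging the participant's own components better?** Same model, k = 3. In the selective cases the effect is placed on the four memory items only (1.25 SD each).

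| Missed tests | f | Kept: fill / own | RMSE: fill / own |
|---|---|---|---|
| Random | 0.2 | 0.94 / 1.00 | 0.238 / 0.248 |
| Random | 0.5 | 0.84 / 1.00 | 0.234 / 0.253 |
| Non-memory | 0.2 | 1.00 / 1.08 | 0.24 / 0.25 |
| Non-memory | 0.5 | 1.00 / 1.21 | 0.22 / 0.28 |
| Memory | 0.2 | 0.84 / 0.87 | 0.25 / 0.26 |
| Memory | 0.5 | 0.60 / 0.67 | 0.30 / 0.30 |

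Own-component averaging removes the shrinkage under random missingness. Under selective missingness it can overstate or understate, and its RMSE is never lower.

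**4. ADAS-Cog rescaling.** With one ADAS-Cog11 item missing, SAP 5.6 multiplies the observed total by between 1 + 5/65 = 1.077 and 1 + 12/58 = 1.207, where Protocol 17.9 would leave the total missing. In the ADAS-Cog14 table the Maze factor is 1 + 12/78 = 1.154. SAP 5.5 scores Maze 0 to 5 on a 90-point total, which gives 1 + 5/85 = 1.059. The printed factor is therefore 1.154/1.059 = 1.09 times what the item range implies, and it equals the Word Recognition factor in the same table.

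**5. Number Cancellation.** The weight is 1/10 in the Cognitive Composite and 1/3 in the Attention Composite. The SAP gives no test, cut-off, visit or formula for D, and does not say who decides. To show that the missing criterion matters, assume no true difference, seven per arm and overdispersed false-alarm counts with mean 2. A Kruskal-Wallis cut of 0.05 would call the three arms unbalanced in about 5% of trials; a rule of a difference of at least 1 between the largest and smallest arm means would do so in about 71%. These are rates of switching metric, not error rates for the treatment comparison.

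**The case against.** Item-level scoring can be regarded as part of deriving a score. Protocol 17.6 says the composites will be derived without saying how, so Protocol 17.9 might be meant only for whole missing assessments. This has some force for the composite. It has little for the ADAS-Cog totals, because SAP 5.6 calls them imputed. On either reading, SAP 11.8 should explain the position.

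A reader might infer that the all-arm fill is a defective method that should give way to own-component averaging. The calculations do not support that. The fill pulls towards no difference, barely moves power or type I error at modest missingness, and has RMSE no higher than the alternative. Own-component averaging is also substitution of the participant's own mean, the same idea as the ADAS-Cog rescaling, so it too would need declaring. This objection stands, and no replacement is proposed.

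A reader might also infer that the Number Cancellation choice will be made by someone who has seen unblinded efficacy results, or that it inflates the type I error. The documents show neither. SAP 5.1 and 5.2 provide for unblinded statisticians who could do the check, and the unblinding statement in SAP 5.3 concerns report listings. The reference to both arms is loose wording, since the next sentence speaks of study arms generally. What remains is that no criterion is stated and nothing places the choice before unblinding. ADAS-Cog totals use the 0 to 5 conversion and are unaffected.

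**Conclusion.** The point holds as a minor one. SAP 11.8 is incorrect as written, because SAP 5.5 and 5.6 both impute where Protocol 17.9 says not to, and the second rule reaches the primary cognitive endpoint. For the Cognitive Composite the consequence is a contrast shrunk by 1 − fk/10, which is 2% to 6% if 20% of participants miss one to three components at random with equal rates across arms. The simulations use a single follow-up visit and assumed correlations, whereas SAP 9.3 specifies a repeated-measures model, so they indicate size only.

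For Number Cancellation, an endpoint definition depends on an unspecified between-arm comparison of a post-randomisation outcome. Its reach is limited to the weights of 1/10 and 1/3, and no error rate can be derived from the documents.

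These are secondary endpoints in a pilot; the safety and synaptic-density analyses are untouched. One caveat applies: SAP 1 refers to protocol Version 1.5, and the version of the protocol supplied cannot be confirmed because its title pages were removed.

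**What to change.** **Missing data.** First check the rescaling tables in SAP 5.6, in particular the ADAS-Cog14 Maze factor against the 0 to 5 item range. Then list the composite fill and the ADAS-Cog11/13/14 rescaling in SAP 11.8 as departures from Protocol 17.9, or amend Protocol 17.9 to permit them. Keep the fill as the main rule. Add a sensitivity analysis of the Cognitive Composite on participants with all ten components, the rule SAP 5.5 already applies to the other three composites.

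**Number Cancellation.** Delete the arm-balance condition. Before unblinding, name one metric for all participants and all visits including baseline, and report another as a sensitivity analysis. Hits minus false alarms is one candidate, since SAP 5.5 already needs it for ADAS-Cog scoring.

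**Cost.** A few sentences in the SAP. The all-ten analysis is less precise: in the simulated setting about 17 of 21 participants and a standard error of about 0.27 rather than 0.24 if 20% are affected, and 10 to 11 participants and about 0.35 if 50% are.

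### SAP 5.5 states the Trail Making sign reversal only for the Cognitive Composite, so the Attention and Executive composites, if programmed literally, mix components that point in opposite directions

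*SAP*

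**What the plan says.** SAP 5.5 (Data Derived by Calculation) builds each z-score by subtracting the baseline mean of all subjects and dividing by the baseline SD. That rule has no sign step. Direction is handled item by item, in the paragraph describing each component.

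- **TMT A and TMT B.** The metric for TMT A is "Time taken for completion". For TMT B the SAP says "The key metric for analysis purposes is again" the same quantity. Both paragraphs carry the sentence "The sign of the z-score for this component will be reversed when deriving the Cognitive Composite score".
- **Maze.** Its paragraph names both the Cognitive and the Attention composite and adds: "The sign of the z-score for this component will be reversed when deriving these composite scores".
- **Number Cancellation.** Provided false alarms are comparable across arms, "we will analyze total hits". No reversal is stated.
- **Category fluency (CFT) and Digit Span.** These count acceptable words and correct trials. No reversal is stated.

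The Attention composite is then "derived using the average of the Number Cancellation, Maze item from ADAS-Cog 14, and TMT A items", and the Executive composite is "derived using the average of the CFT, Digit Span, and TMT B items". Neither definition contains a sign rule or refers back to the Cognitive Composite. The Memory definition does refer back, by describing itself as similar to it. Protocol 17.6 adds only that the composites come from the clinical outcome measures.

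Both composites are secondary endpoints (protocol 6.2.2, SAP 4.6). They are analysed by the mixed model in SAP 9.3 and used in the Pearson correlations in SAP 9.4.

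**The concern.** A composite of z-scores can be interpreted only if all its components run the same way. Section 5.5 is the specification a programmer works from. Followed exactly, it leaves TMT A running against the other two Attention components and TMT B running against the other two Executive components. Improvement on Trails would then cancel improvement elsewhere in the same score. Two programmers could also produce different scores from the same text, one carrying the reversal over and one not. With about 7 participants per arm (protocol 17.2), there is little information to lose in this way.

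**Working it through.** The plan gives no figure for this point, so there is none to reproduce. The check follows the signs and then sizes the consequence.

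**Step 1. Signs under the rules as written** (+ means higher is better; source SAP 5.5)

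| Composite | Component | Raw direction | Reversal stated for this composite? | Result |
|---|---|---|---|---|
| Attention | Number Cancellation (hits) | + | none | + |
| Attention | Maze | − | yes | + |
| Attention | TMT A (time) | − | no | − |
| Executive | CFT (words) | + | none | + |
| Executive | Digit Span (trials correct) | + | none | + |
| Executive | TMT B (time) | − | no | − |

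In the Cognitive Composite, three components are naturally + and seven are reversed, so all 10 align. The four Memory items are all higher-is-worse. They are all − if unreversed and all + if reversed, so nothing cancels, and only the overall direction is left unstated.

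**Step 2. Shift in the score.** Let d be an improvement in baseline-SD units. Because the z-scores use a fixed baseline mean and SD, this arithmetic applies equally to change from baseline.

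- All three components improve by d: aligned (d + d + d)/3 = d; literal (d + d − d)/3 = d/3.
- Only Trails improves by d: aligned (0 + 0 + d)/3 = +d/3; literal (0 + 0 − d)/3 = −d/3. The sign flips, and no assumption about correlation is needed.
- Only the two other components improve by d: 2d/3 either way, so the shift is unaffected.

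**Step 3. Standardised effect.** The literal score also has a different SD, so the shift alone does not measure what is lost. Assumptions, none given in the documents: unit variances, the same d on each component, and a common correlation r between the components once aligned.

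- SD of the aligned sum = √(3 + 6r); standardised effect = 3d/√(3 + 6r).
- SD of the literal sum = √(3 − 2r); standardised effect = d/√(3 − 2r).
- Ratio, literal to aligned = √(3 + 6r) / (3√(3 − 2r)).

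| r (assumed) | Calculation | Share of aligned effect kept |
|---|---|---|
| 0 | √3.0 / (3√3.0) | 0.33 |
| 0.3 | √4.8 / (3√2.4) | 0.47 |
| 0.5 | √6.0 / (3√2.0) | 0.58 |
| 0.7 | √7.2 / (3√1.6) | 0.71 |

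The same ratio applies to the SAP 9.4 correlations when an outside variable has the same correlation with each aligned component.

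**The case against.** The best reply is that the intended reading is easy to recover. Section 5.5 defines each component's z-score once and then gives three consecutive domain-composite definitions, the first of them modelled on the Cognitive Composite. A programmer who sees that Trails is a time would probably reuse the reversed z-score. That is a fair account of what the authors meant. It does not settle the matter, because the reversal is expressly tied to one composite and the Attention and Executive definitions do not refer back.

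A reader might infer from the Maze paragraph, which names Attention, that the narrower Trails wording was a deliberate choice. The documents do not support that. Six of the seven reversed items (Word Recall, Orientation, Delayed Word Recall, Word Recognition, TMT A, TMT B) name only the Cognitive Composite. The four ADAS-Cog items among them also feed the Memory composite. Maze is the exception, and the pattern points to an omission.

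It also stands that the exposure is limited. The primary objective is safety (SAP 4.2), the sample size rests on PET (SAP 4.5), and ADAS-Cog11 is named the primary cognitive endpoint (SAP 5.5). A Trails effect would still be visible elsewhere: total Trail A plus Trail B time has its own mixed-model analysis (SAP 9.3), and the individual battery items enter the correlations (SAP 9.4).

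**Conclusion.** The text is wrong as written for two secondary endpoints, most likely through a drafting omission. Attention and Executive each combine two higher-is-better components with one higher-is-worse component if the SAP is programmed literally. The sign conflict, and the reversal of a Trails-only benefit, follow from the text alone.

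The retained effect of about 47%, 58% or 71% at r = 0.3, 0.5 or 0.7 is illustrative. It rests on equal improvement, equal variances and a common correlation. The planned analysis uses change from baseline with a baseline covariate, so the relevant variances and correlations are those of the adjusted changes, which the documents do not give.

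A reader might take the drop from d to d/3 as a two-thirds loss of detectable effect. That holds only at r = 0; at r of 0.3 to 0.7 the standardised loss is 53% to 29%. Nor does the point reach the primary endpoint or the Cognitive Composite. It should be fixed, but it does not threaten the trial's main conclusions.

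**What to change.** Add one sentence to SAP 5.5: the z-scores of all higher-is-worse components (Word Recall, Orientation, Delayed Word Recall, Word Recognition, Maze, TMT A and TMT B) are reversed in every composite in which they appear, so that a higher value is better for all composites. This settles Attention and Executive and also fixes the direction of Memory.

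The cost is that sentence and a check of the derivation program. No data collection, model or sample size changes. It should be done before unblinding, when it is a clarification. Made afterwards, a choice of sign for an endpoint component could be challenged as driven by the results.
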